5. STEMI
6. NSTEMI/UA
7. Chronic kidney disease (creatinine clearance < 60 ml/min/1.73m²)
8. Gender
9. Prior TIA or stroke
10. Low body weight (< 60 kgs)

3.3.4. Variables

The primary dependent variable will be MACE (composite of all-cause death, non-fatal MI, stroke or unplanned coronary revascularization) through 90 days from hospital admission for the index PCI. Secondary dependent clinical and economic variables will include components of MACE, bleeding, rehospitalizations for relevant CV events and associated DRG costs, and index hospital length of stay. Other clinical and economic variables of interest will be defined in the Statistical Analysis Plan (SAP). The primary independent variable will be treatment cohort (prasugrel versus clopidogrel) and other independent variables (covariates) will include baseline demographic and clinical characteristics, and baseline treatment utilization.

The variables and their definitions collected for the analysis dataset are listed in [Attachment 1](#).

3.4. Plan of Analysis

3.4.1. Methods

Analyses comparing outcomes of interest between prasugrel and clopidogrel groups will be conducted unadjusted and adjusted (using inverse probability weight [IPW] method) for demographic, clinical, and procedural differences as described below. The primary comparison will be between patients treated with prasugrel versus clopidogrel in an intention-to-treat (ITT) fashion, after adjustment for demographic, clinical, and procedural differences as described below. The primary endpoint of interest is the first occurrence of MACE within 90 days from hospital admission for the index PCI. For the primary outcome of interest, the crude unadjusted 90-day rates of MACE will be calculated for each group using the Kaplan-Meier method, also including index hospital events. Crude rates will be compared between groups using the log-rank test (Kalbfleisch et al. 1980; Prentice et al. 1978).

For descriptive purposes, baseline clinical (including laboratory evaluations) and demographic and procedural characteristics will be compared between groups using student's t-test and chi-square test for continuous and categorical variables, respectively.

In-hospital (that is, post-procedural) outcomes will be assessed by comparing the proportion of post-procedural events between prasugrel and clopidogrel groups. These binary proportion comparisons will be performed using a Chi-square test between groups.

Total follow-up for each patient in Study B020 will be defined as time until death, last follow-up or 365 days following hospital admission for the index PCI, whichever comes first. To evaluate the associations between treatment group (prasugrel versus clopidogrel) and dependent outcomes, hazard ratios will be calculated using Cox proportional hazards regression. Median event free survival time will also be reported. In addition to age, gender and race, any baseline demographic, clinical, or procedural characteristic demonstrating a significant ($p < 0.1$) difference between groups will be included in the multivariable model. The model will also include other covariates that might be pertinent to the clinical outcome even if there are no significant differences in this cohort (for example, diabetes mellitus [DM], smoking status, etc.). Using these candidate covariates, a final multivariate model will be generated using a stepwise selection procedure to ensure model parsimony. The primary exposure of interest (prasugrel versus clopidogrel) will be forced in this final model.

As a separate sensitivity analysis, IPW will be used to adjust the selection bias for the treatment allocation. The propensity score will be generated using a non-parsimonious logistic regression model with the dependent variable as prasugrel versus clopidogrel treatment. From this model, each patient will be ascribed a predicted probability that reflects the propensity to have received prasugrel or clopidogrel at discharge. Inverse probability weights will be derived for all observations using the propensity scores, and then regression analyses will be repeated using these weights.

The primary analysis will include the overall ACS/PCI population. All analyses will be repeated in the all subgroups listed in Section 3.3.3.

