3.4.2.2. Adjusted Outcomes Analyses

To examine the associations between treatment group (prasugrel versus clopidogrel) and dependent categorical resource use outcomes (for example, rehospitalizations for CV events), hazard ratios will be calculated using Cox proportional hazards regression. Models will be constructed as described previously in Section 3.4.1.

For analyses of costs, length of stay, and other continuous economic outcomes, IPW will be used. Each patient who received prasugrel or clopidogrel will be weighted by the inverse of the probability of receiving prasugrel. The propensity score and inverse probability weights will be derived as described previously in Section 3.4.1.

Due to the unknown distribution of continuous economic outcomes and the skewness of the data (especially direct and indirect costs), the comparison of continuous outcomes between cohorts will be conducted using non-parametric bootstrapping on IPW adjusted differences in means costs. A 95% confidence interval for the IPW-adjusted cost in both groups and difference in mean costs between the groups will be obtained based on percentiles of the bootstrap distribution. The primary independent variable will be treatment cohort (prasugrel versus clopidogrel) and other independent variables (covariates) will include baseline demographic and clinical characteristics, and baseline treatment utilization.

Differences in healthcare resource utilization and related costs between patients treated with prasugrel versus clopidogrel will be assessed for 1) the ACS-PCI subgroup with no prior stroke or TIA (primary economic outcomes analysis population) and 2) the overall ACS-PCI population (economic outcomes analysis subgroup), and additional subgroups may be considered. As a separate sensitivity analysis, a Generalized Linear Model (with gamma specification and log link function) will be used to model costs between treatment groups. The primary independent variable will be treatment cohort (prasugrel versus clopidogrel) and other independent variables (covariates) will include baseline demographic and clinical characteristics, and baseline treatment utilization.

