3.4.5. Multiplicity

The primary endpoint of interest in the present study is 90-day MACE, for which a Type I error rate of 0.05 will be used. All other endpoints are secondary and therefore no multiplicity adjustments will be performed.

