3.4.7. Robustness

The primary analysis will involve multivariate Cox proportional hazards regression as described above. The analysis will incorporate a step-wise selection procedure to generate a parsimonious model with selected covariates. Several sensitivity analyses will be performed to ensure that the primary findings are robust. First, select covariates will be selected using different approaches (forward and backward selection) to assess whether or not the association for the primary variable of interest changes substantially. Second, all analyses will be repeated in an IPW-adjusted cohort.

These additional analyses are meant to be confirmatory (that is, yield approximately the same answer) to the primary analysis.

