3.4.8. Sample Size and Power Considerations

Study B020 is designed to assess the difference in MACE associated with prasugrel versus clopidogrel in patients presenting with ACS managed with a PCI from academic centers in the US from 01 January 2010 to 30 June 2013. Data from the Premier study and from TRANSLATE-ACS have suggested that the MACE rate at 90 days will be approximately 8.0%. Using 8.0% as the control rate, it is expected that the relative reduction with prasugrel will be

20% lower than with clopidogrel (hazard ratio 0.80). To achieve 80% power with an alpha of 0.05, and factoring in a 10% patient drop-out, at least 4,303 patients on prasugrel and clopidogrel need to be enrolled, yielding a minimum enrollment of 8,606 patients. If it is necessary to extend the window of time beyond 30 June 2013 in order to enroll an adequate number of patients, no protocol amendment will be required.

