The adjusted associations between exposure groups and the primary MACE outcome will then be calculated using Cox proportional hazards regression. This model will include the following two covariates: exposure group (prasugrel versus clopidogrel) and study center, with propensity group entered as a stratification variable.

The following sensitivity analyses for the primary MACE outcome will also be performed:

1. Covariate adjustment. Hazard ratios for the primary MACE outcome associated with prasugrel versus clopidogrel treatment will be generated using a fully-fitted Cox proportional hazards regression model. In addition to age, , gender and study center, this model will include all baseline covariates demonstrating significant differences ($p < 0.05$) between groups. Other baseline variables that may be plausibly related to the primary outcome will also be included: BMI, race, diabetes mellitus, serum creatinine, hemoglobin, prior MI, prior CHF, prior PAD, prior cerebrovascular disease, multivessel disease, CAD presentation (unstable angina vs. nstemi vs. stemi), current smoking, number of stents implanted, stent type and stent diameter (maximum). A second covariate-adjusted model will be generated using forward stepwise regression with treatment forced in first.

2. Propensity matching: A 1:1 matched cohort will be derived from the overall sample using the propensity scores as described above. Matches will be generated using nearest neighbour matching without replacement (Austin 2011).

3. Equipoise Analysis: From the overall cohort, an 'equipoise' subgroup will be derived that includes all patients with preference scores ranging between 0.4 – 0.6. These patients are assumed to have a reasonable high probability of being assigned to either treatment (Walker et al., 2013).

4. Inverse Probability Weight Analysis: Inverse probability weights (IPW) will be derived for all observations using the propensity scores. Observations with propensity scores exceeding the 95th percentile or below the 5th percentile for the

entire cohort will be excluded (trimmed) for purposes of this specific analysis. After trimming regression analyses will be performed using these weights.

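### Stepwise selection in the Protocol's Cox model can delete confounders the plan has itself identified; the SAP's primary analysis avoids this, but one SAP sensitivity model and the Protocol text do not

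*Protocol*

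**What the plan says.** **Protocol.** Section 3.4.1 opens by naming inverse probability weighting (IPW) as the adjustment, but later makes IPW a separate sensitivity analysis. The main adjusted analysis is a Cox model. Its candidates are age, gender, race, every baseline characteristic that differs between drugs at p<0.1, and other clinically pertinent covariates. From these, "a final multivariate model will be generated using a stepwise selection procedure to ensure model parsimony". Only treatment is forced in. No direction, entry or stay threshold, or other criterion is given.

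Section 3.4.7 confirms that this is the primary analysis: "The analysis will incorporate a step-wise selection procedure to generate a parsimonious model with selected covariates". Its robustness checks are forward and backward selection and a repeat with IPW, where the propensity model is non-parsimonious. Section 3.4.2.2 says of the Cox models for rehospitalization: "Models will be constructed as described previously in Section 3.4.1".

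**SAP.** Sections 6.1 and 6.7 make the primary analysis a Cox model stratified by propensity strata, with drug and center as covariates and no stepwise step. Sensitivity analysis 1 in 6.1 is a fully fitted Cox model containing age, gender, center, all covariates that differ at p<0.05, and 15 further named covariates. It then adds: "A second covariate-adjusted model will be generated using forward stepwise regression with treatment forced in first". Section 6.7 describes the additional analyses as confirmatory.

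**The concern.** In a non-randomised comparison the covariates are there to remove confounding. Confounding by a covariate depends on two things together: its imbalance between drugs and its effect on outcome. Stepwise selection, as usually run, looks only at the second. A covariate that is clearly imbalanced but weakly prognostic tends to be dropped, and its share of the confounding goes back into the drug effect. Protocol 3.4.3 itself expects significant baseline differences between the groups.

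The reported interval treats the selected model as if it had been fixed in advance. Forward and backward reruns select in the same way, so their agreement with the main model gives little reassurance. Protocol 3.4.6 plans multiple imputation of baseline data, and no rule covers selection that differs between imputed datasets.

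At stake is the type I error of the adjusted MACE comparison, "for which a Type I error rate of 0.05 will be used", and the credibility of any covariate-adjusted hazard ratio that comes from a selected model.

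**Working it through.** **1. Planned events.** Protocol 3.4.8 gives 8,606 patients, "Using 8.0% as the control rate", a hazard ratio of 0.80 and 10% drop-out. Rates of 8.0% and 6.4% average 7.2%.

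- With drop-out: 8,606 x 0.9 x 0.072 = 558 events.
- Without drop-out: 8,606 x 0.072 = 620 events. With drop-out and no drug effect (8.0% in both groups) the figure is also 8,606 x 0.9 x 0.08 = 620.

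The plan's own sample size is stated as "To achieve 80% power with an alpha of 0.05, and factoring in a 10% patient drop-out", giving 4,303 per group. It is not reproduced. The pooled two-proportion formula (two-sided alpha assumed) gives 4,096, and 4,096/0.9 = 4,552. That is a separate matter; the event count used here follows from the stated N.

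**2. Can the events carry a full model?**

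| Covariate parameters | Events per parameter, 558 events | 620 events |
|---|---|---|
| 30 | 18.6 | 20.7 |
| 40 | 13.9 | 15.5 |
| 66 | 8.4 | 9.4 |

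The 66 is a count of all pre-procedure, admission-drug and procedural fields in Attachment 1. Peak, nadir and discharge fields are left out as post-treatment. For 30-40 parameters parsimony is not needed; at 66 it is thinner.

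**3. Why weak confounders are lost.** For a standardised covariate the standard error of its log hazard ratio is about 1/√558 = 0.0423. At a log hazard ratio of 0.05 per SD the expected z is 0.05/0.0423 = 1.18. The chance of retention at p<0.05 is P(Z > 0.78) + P(Z < -3.14) = 22%, however imbalanced the covariate is. At 0.20 per SD the expected z is 4.7, and it is nearly always kept.

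**4. A hand calculation.** Take 15 independent covariates, each with log hazard ratio 0.05 per SD and shifted 0.2 SD between drugs in the same harmful or protective direction.

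- Average estimated coefficient lost per covariate: E[z; |z|<1.96] x 0.0423 = 0.631 x 0.0423 = 0.0267.
- Bias in the drug log hazard ratio: 15 x 0.2 x 0.0267 = 0.080, a hazard ratio of 1.083 (or its reciprocal).
- Standard error of the drug effect with equal groups: 2/√558 = 0.0847. The shift is 0.080/0.0847 = 0.95 standard errors.
- Rejection of a true null: P(Z > 1.01) + P(Z < -2.91), about 16%.

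**5. Simulation at a true hazard ratio of 1.** Estimates were drawn from their large-sample normal distribution (information = events x covariance), with backward elimination at p<0.05 and treatment forced, 1,500-4,000 runs per scenario. Weak means log hazard ratio 0.05-0.08 per SD; imbalance is 0.1-0.3 SD. The full model rejected in 3.5-6.5% of runs throughout.

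| Scenario (independent covariates) | Rejection after selection |
|---|---|
| 5 weak confounders, one direction | 4-12% |
| 10 weak, one direction | 5-21% |
| 15 weak, one direction | 8-34% |
| 20 weak, one direction | 10-46% |
| 10-20 weak, mixed directions | 6-13% |
| Strong only (0.20 per SD) | 5.2% |
| Weak, one direction, stay level 0.20 instead of 0.05 | about 5-16% |

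A patient-level logistic check of the case in step 4 (n = 7,745, 400 runs) gave 15.5% with 30 candidates and 19.3% with 66. The full model gave 4.8% and 5.8%.

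**6. Effect of correlation.** Four covariates were set at 0.30 per SD and the rest at 0.05, all shifted one way, with entry and removal at p<0.05. The independent row used 2,000 runs per cell, the others 800.

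| Pairwise correlation | 20 candidates, shift 0.15 SD | 30 candidates, shift 0.20 SD |
|---|---|---|
| 0 | 12.2% | 35.8% |
| 0.1 | 5.6% | 7.5% |
| 0.2 | 5.2% | 7.2% |
| 0.3 | 5.9% | 5.6% |

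Retained covariates stand in for dropped ones, so most of the inflation disappears.

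**The case against.** The strongest reply is that the analysis has been superseded. The SAP's primary model has no stepwise selection, its strata are formed blind to outcome, and its fully fitted Cox model is what one would ask for. The forward stepwise model is only a second version beside it, where a divergence could be seen. The Protocol also plans IPW from a non-parsimonious propensity model. All of this stands. A reader might infer from the Protocol that the study's primary result rests on stepwise selection; under the SAP it does not.

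Three things remain. SAP Table 4 has one covariate-adjusted column, and its footnote does not say which of the two covariate models fills it; nor does the SAP text on secondary outcomes. The IPW analysis is only a sensitivity analysis in the Protocol. The readmission models have no methods text except Protocol 3.4.2.2, because SAP 6.2 is deferred to an addendum that was not available. The Table 5 listing does mention a propensity-adjusted hazard ratio for categorical economic outcomes, so the stepwise route there may also have been dropped.

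A reader might also infer that type I error is inflated by a fixed multiple, say 2-5 times. The documents do not support that. They give no stepwise criterion and no number, strength, size or direction of imbalances, and steps 5 and 6 show that the answer depends on all of these and on correlation. Many Attachment 1 fields are plainly related (diabetes and insulin use; prior MI, PCI and CABG; stent number and length), although uniform positive correlation is itself a favourable assumption.

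**Conclusion.** The concern holds for the Protocol's MACE model, for readmission models built from it, and for the SAP's forward stepwise sensitivity model. It does not reach the SAP's primary analysis. Selection can remove covariates that the plan has flagged as imbalanced or pertinent, with no gain, since about 558 events support 30-40 parameters comfortably.

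Assuming p<0.05 for entry and stay, type I error ranges from about nominal (correlated covariates, few weak confounders, or strong ones only), through about 6-13% (mixed directions), to above 40% (many independent weak confounders in one direction). The full model stays at about 5%. The upper end needs assumptions that the documents neither state nor exclude, so the case for change rests on the mechanism and the low cost, not on any single figure.

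**What to change.** - Delete stepwise, forward and backward selection from Protocol 3.4.1 and 3.4.7, and so from 3.4.2.2. Delete the second model from sensitivity analysis 1 in SAP 6.1.
- Keep the SAP's fully fitted model as the only covariate-adjusted Cox model, with drug, center and a list of pre-treatment covariates fixed by name. SAP Table 1 shows peak and nadir laboratory values and discharge drugs among the baseline characteristics; leave these off the list.
- State in both documents that the SAP's propensity-stratified model is primary.
- State that the full model fills the covariate-adjusted column of Table 4 and serves as the covariate-adjusted analysis for secondary outcomes.
- Before fixing the list for readmission, component and subgroup models, check the parameter count against the expected events. These have fewer events than overall MACE.

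The cost is wording, with fewer models to run, and a somewhat wider interval for the drug effect. For K independent covariates each shifted by s SD, the standard error relative to no adjustment is about √(1 + K s²/4). That is √1.05 = 1.02 for 20 covariates at 0.10 SD and √1.47 = 1.21 for 30 at 0.25 SD. Stepwise keeps some covariates, so the increase relative to it is smaller.

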3.4.2. Economic Outcomes Analyses

3.4.2.1. Unadjusted Outcomes Analyses

Data will be gathered on all patients in the study concerning their index and follow-up hospitalizations for MI, stroke, repeat unplanned coronary revascularization and stent thrombosis. The frequency of PCI and/or coronary artery bypass graft (CABG) procedures during these hospitalizations will be captured. The proportion of patients with follow-up hospitalization for these diagnoses will be compared between prasugrel and clopidogrel groups using Chi-square tests. The crude unadjusted rates will be calculated for each group using the Kaplan-Meier method and compared using the log-rank test.

All hospitalizations (except for bleeding-related hospitalizations) will be assigned a DRG based on the diagnoses of interest without knowledge of the patient's treatment assignment. The DRGs will be converted to direct medical costs for hospitalization based on Medicare Part A reimbursement. Bleeding-related rehospitalization costs will not be included in this specific analysis as the specific DRG related to this type of admission cannot be determined in this dataset. An additional cost for physicians will be estimated using the Resource-Based Relative

Value Scale (RBRVS) and the Medicare payment schedule. When a hospitalization includes more than 1 event, the highest paying DRG will be used.

Total direct medical costs for the index hospitalization and subsequent hospitalizations will be totaled. Indirect costs (lost productivity) due to premature CV death will be calculated. Hospital length of stay will be calculated as the number of days from hospital admission to discharge. The difference in mean costs (direct and indirect), length of stay, and other continuous resource utilization outcomes (for example, counts of CV-related hospitalizations per patient) between treatment groups will be calculated using t-tests. Exact tests, bootstrapping and/or nonparametric tests will be used as appropriate.

In Study B020, clinical outcomes are measured by days from index hospital admission whereas health economic outcomes are measured by days from index hospital discharge.

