 5. STEMI
 6. NSTEMI/unstable angina (UA)
 7. Chronic kidney disease (creatinine clearance < 60 ml/min/1.73m²)
 8. Gender
 9. Prior stroke or TIA
 10. Low body weight (< 60 kgs)
2. To compare the following economic outcomes (health resource utilization and costs) in patients treated with prasugrel versus clopidogrel for ACS patients with no prior TIA or stroke and managed with PCI (primary economic outcomes analysis population), and the overall ACS/PCI population (economic outcomes analysis subgroup):
 - a. Length of stay for index hospitalization
 - b. Readmission rates for MI, bleeding, stroke, unplanned coronary revascularization, or stent thrombosis at 30, 90, 180, and 365 days following index hospital discharge

- c. Health resource costs at 30, 90, 180, and 365 days following index hospital discharge
- d. Lost productivity due to cardiovascular death

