3.3. Research Design

3.3.1. Study Design

Study B020 is designed as a retrospective cohort study evaluating data for patients presenting with ACS managed with a PCI from 6 to 12 academic centers in the US from 01 January 2010 to 30 June 2013, with any follow-up data available for analysis. This study will evaluate the comparative effectiveness and economics of prasugrel relative to clopidogrel in approximately 8,600 patients (minimum 4,300 receiving prasugrel) in a usual care environment from academic centers in the US. These academic centers maintain institutional databases related to baseline characteristics, procedural characteristics and clinical and economic outcomes during and following index hospitalization of patients with ACS undergoing PCI.

The participating academic centers will run a query in their ACS-PCI database to identify all patients who received prasugrel or clopidogrel between 01 January 2010 and 30 June 2013. The study period was selected based on the approval and steady availability of prasugrel in the US market at the end of 2009 and by the need for a study with a minimum 90-day follow-up in this population. The primary endpoint of the study will be at 90 days from index hospital admission; at this point in therapy, the adherence rate is expected to continue to be high while the switching rate is expected to be low ($\leq 10\%$).

Figure 1 illustrates the study time periods.

Abbreviations: ACS = acute coronary syndromes; PCI = percutaneous coronary intervention.

Figure 1. Study B020 design for patients with ACS managed with PCI and treated with prasugrel or clopidogrel between 01 January 2010 and 30 June 2013.

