5.1 Study Design

Study B020 is designed as a retrospective cohort study evaluating data for patients presenting with ACS managed with a PCI from 8 academic centers in the US from 01 January 2010 to 30 June 2013, with any follow-up data available for analysis. The centers include: Mount Sinai Medical Center, Intermountain Heart Institute, Duke University, Cleveland Clinic Foundation, University of Pittsburgh, University of Minnesota, Christiana Health Care and Aurora Research Institute. This study will evaluate the comparative effectiveness and economics of a treatment strategy initiating prasugrel relative to clopidogrel in approximately 8,600 patients (minimum 4,300 receiving prasugrel) in a usual care environment from academic centers in the US. These academic centers maintain institutional databases related to baseline characteristics, procedural characteristics, and clinical and economic outcomes during and following index hospitalization of patients with ACS undergoing PCI.

The participating academic centers will run a query in their ACS-PCI database to identify all patients who received prasugrel or clopidogrel between 01 January 2010 and 30 June 2013. The study period was selected based on the approval and availability of prasugrel in the US market at the end of 2009 and by the need for a study with a minimum 90-day follow-up in this population. The primary endpoint of the study will be at 90 days from index PCI; at this point in therapy, the adherence rate is expected to continue to be high while the switching rate is expected to be low ($\leq 10\%$). Figure 1 illustrates the study time periods

[figure not shown]

Figure 1 Study B020 design for patients with ACS managed with PCI and treated with prasugrel or clopidogrel between 01 January 2010 and 30 June 2013.

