6.8 Sample Size and Power Considerations

Study B020 is designed to assess the difference in MACE associated with prasugrel versus clopidogrel in patients presenting with ACS managed with a PCI from academic centers in the US from 01 January 2010 to 30 June 2013. Data from the Premier study and from TRANSLATE-ACS have suggested that the MACE rate at 90 days will be approximately 8.0%. Using 8.0% as the control rate, it is expected that the relative reduction with prasugrel will be 20% lower than with clopidogrel (hazard ratio 0.80). To achieve 80% power with an alpha of 0.05, and factoring in a 10% patient drop-out, at least 4,303 patients on prasugrel and clopidogrel need to be enrolled, yielding a minimum sample size of 8,606 patients. If it is necessary to extend the window of time beyond 30 June 2013 in order to enroll an adequate number of patients, no protocol amendment will be required.

7 General Considerations

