7.1 Multi-center Studies

Data will be gathered on all patients in the study concerning their index and follow-up hospitalizations for acute myocardial infarction, stroke, repeat unplanned coronary revascularization, and stent thrombosis. All hospitalizations will be assigned a DRG based on these diagnoses. When a hospitalization includes more than one event, the highest paying DRG will be used. Total hospitalization costs and hospitalization costs after the index hospitalization will be totaled. The difference in

mean hospital costs by treatment are will be assessed and the 95% CI (confidence interval) assessed by bootstrap analysis.

Data will be gathered on all patients in the study that meet the inclusion criteria in between January 1ST, 2010 to June 30TH, 2013.

Each center will provide events according to the following rules:

- Patient level data. In case of a subject undergoing multiple procedures within the time frame of the study we will abstract relevant clinical, demographic and procedural details from the first procedure only
- In case of multiple events of a given type only the first event will be reported for purposes of survival analyses.

Detailed technical instructions will be provided to each site in order to extract the relevant data from each database prior to exporting to the data coordinating center.

8 Summary of Study Data

All summary tables will be organized in columns for each treatment (Prasugrel/Clopidogrel) and overall and will be annotated with the total population size relevant to that table/treatment, including any missing observations.

Total, mean, SD (standard deviation), median, min, and max will be specified for continuous data frequency and percentage (based on the non-missing sample size) of observed levels will be reported for all categorical data.

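### Costs at 180 and 365 days are compared as plain or treatment-weighted means, with no stated correction for incomplete follow-up

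*Protocol*

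**What the plan says.** Protocol 3.2.2 lists among the economic objectives "Health resource costs at 30, 90, 180, and 365 days following index hospital discharge". The mock healthcare cost table in SAP section 12 has matching rows, including 180-day, 1-year and 1-year aggregate costs.

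Follow-up is less certain than those horizons. Protocol 3.3.1 explains the study period in part "by the need for a study with a minimum 90-day follow-up in this population" and otherwise takes patients "with any follow-up data available for analysis"; SAP 5.1 repeats the 90-day minimum. Follow-up stops at death, at last contact, or at one year, counted from admission in Protocol 3.4.1 and from index PCI in SAP 4.3. Protocol 3.4.2.1 counts economic outcomes from discharge.

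The cost method is to assign DRG costs to the recorded hospitalizations, add them up and compare means. Protocol 3.4.2.1 applies t-tests to "The difference in mean costs (direct and indirect), length of stay" and other continuous outcomes, with exact, bootstrap or nonparametric tests as appropriate. Protocol 3.4.2.2 uses "non-parametric bootstrapping on IPW adjusted differences in means costs", with a gamma GLM as sensitivity analysis. SAP 7.1 also totals the hospitalization costs and says of the comparison: "mean hospital costs by treatment are will be assessed and the 95% CI (confidence interval) assessed by bootstrap analysis".

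Rehospitalization rates, in the same two protocol sections, are analyzed by Kaplan-Meier, log-rank and Cox. Protocol 3.4.6 and SAP 6.6 do not impute missing outcomes. SAP 6.2 is an empty heading whose content is assigned to Addendum 1.

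**The concern.** The plan treats follow-up as censored for rehospitalization events but not for the costs that those events generate. A patient last seen on day 120 has an unknown 365-day cost. The text gives two possible treatments without choosing: keep the partial total, or set the cost to missing and drop the patient. The first understates the mean. The second is sound only if loss is unrelated to cost.

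The inverse probability weights in Protocol 3.4.2.2 model which drug the patient received, not whether the patient stayed under observation. They leave the problem where it was, and so does the gamma GLM.

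At stake are the 180- and 365-day cost means and the cost difference between the drugs, which are secondary economic results.

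**Working it through.** The documents state no cost figure to reproduce, so this is an illustration of size.

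**Inputs from the documents.** Horizons H = 180 and 365 days from discharge; minimum follow-up 90 days; index dates 1 January 2010 to 30 June 2013 (1,277 days). SAP 6.8 speaks of "factoring in a 10% patient drop-out", but as an allowance in the sample size for 90-day MACE. No loss figure is given for 180 or 365 days.

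**Assumptions.** Post-discharge cost accrues evenly; a share c of patients is lost; cost after loss counts as zero.

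**1. Understatement within one arm.**
- All lost at day 90: retained share = 1 − c(H − 90)/H.
- Loss spread evenly from day 90 to H: retained share = 1 − c(H − 90)/(2H).

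| c | H | all at day 90 | spread from day 90 |
|---|---|---|---|
| 10% | 180 | 1 − 0.10 × 90/180 = 95.0% | 97.5% |
| 10% | 365 | 1 − 0.10 × 275/365 = 92.5% | 96.2% |
| 30% | 180 | 85.0% | 92.5% |
| 30% | 365 | 77.4% | 88.7% |

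Early accrual softens this. If half the 365-day cost falls in the first 90 days, 10% loss at day 90 keeps 1 − 0.10 × 0.5 = 95%.

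**2. Effect on the difference.** With the same retained share k in both arms, the observed difference is k times the true one: shrunk, with nothing false created. With unequal loss spread over the whole year, the retained share is 1 − c/2. Loss of 5% gives 0.975 and 15% gives 0.925, a false difference of 0.05 of the true mean post-discharge cost. For a total of index cost I plus post-discharge cost P, that proportion is multiplied by P/(I + P), because index cost is fully observed.

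**3. Simulation with equal true costs.** It used 400,000 patients per arm, a mean of 0.15 admissions a year at 20,000 each, and loss unrelated to cost spread over days 90 to 365 (all assumed). With 30% versus 10% loss:

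| | 30% loss | 10% loss |
|---|---|---|
| true mean | 2,992 | 2,986 |
| observed totals | 2,655 | 2,872 |
| unweighted exclusion | 2,996 | 2,980 |
| censoring weights | 2,994 | 2,985 |

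Exclusion does well here only because loss was made unrelated to cost.

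**4. Mismatched clocks.** Under the protocol, a stay of L days pushes the end of the 365-day cost window to day 365 + L from admission, while follow-up stops at day 365. The unseen share is L/365, or 1/365 = 0.27% per day of stay. Under the SAP, L becomes the days from PCI to discharge. This is small, but it occurs even with perfect retention, and it grows with length of stay, which is itself a compared outcome.

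**5. Administrative censoring.** This depends on the data cut-off, which is not stated. In the worst case, a cut 90 days after 30 June 2013 with even enrolment, (180 − 90)/1,277 = 7.0% of patients lack 180 days and (365 − 90)/1,277 = 21.5% lack 365. With a cut at about mid-2014 or later, essentially none do. That date moves later if enrolment is extended, as Protocol 3.4.8 and SAP 6.8 allow.

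**The case against.** The strongest reply is that the governing text is missing. SAP 6.2 places the economic methods in Addendum 1, and a mean difference with a bootstrap interval, as in SAP 7.1, is compatible with censoring-weighted means. This stands as a caveat. It does not change what the protocol sections say, which is to total observed admissions and weight for treatment only.

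A reader might infer that lost patients are certain to be counted as cheap. The documents do not say so. The mock cost table carries N Missing rows at each horizon, and missing outcomes are not imputed, so exclusion is possible. Those rows are generic to the table template, so they do not settle it. If patients are excluded, the partial-total percentages no longer apply, and the question becomes whether loss is related to cost.

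A reader might also infer heavy censoring by the calendar, or a false saving for prasugrel from rising uptake. Neither is supported. The SAP cites material dated September and November 2014, still describes extraction as future work, and defines its outcome fields as within one year of the procedure. All of this points to a cut late enough for nearly everyone. No passage reports rising prasugrel enrolment or different loss by arm, and the 10% allowance is not a forecast of loss at one year.

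Finally, the censoring date is the last recorded encounter, and these databases do not typically hold outpatient encounters (Protocol 3.3.2, SAP 5.2). If that date is driven by events, censoring weights would give too much weight to rehospitalized patients. The same weakness affects the planned Kaplan-Meier and Cox analyses. It calls for a check and does not defeat the correction.

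**Conclusion.** The concern holds in a limited form. As written, the plan has no method for incomplete follow-up in 180- and 365-day costs, and its treatment weights do not provide one. Late post-discharge means can be understated or selectively estimated. The difference between drugs is falsely shifted only if loss, or its relation to cost, differs by arm.

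The size cannot be known from the documents. The illustrative figures, about 4% to 7.5% understatement at 365 days with 10% loss after day 90 and about a 5% false difference with 5% versus 15% loss, rest on even accrual, zero cost after loss and loss rates that the plan does not give. They apply to post-discharge cost, not to totals that include the index stay. The 21.5% figure is a worst case only.

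The one economic hypothesis (Protocol 3.2.3) concerns 30 days from discharge and is largely unaffected. This is a cheap improvement to secondary results, not a threat to the study.

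**What to change.** In Protocol 3.4.2 or Addendum 1:

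- State the data cut-off and the rule for patients whose cost window is incomplete.
- Start the cost window and the follow-up cap from the same date.
- For 180- and 365-day costs, include only patients whose index date allows the full window before the cut-off. Select on the index date, not on the follow-up achieved.
- Among them, apply inverse-probability-of-censoring weights for loss to follow-up, multiplied by the treatment weights. Re-estimate both sets of weights in each bootstrap sample. Treat death as complete follow-up.
- Before using the last-encounter date as the censoring date, check that it is not driven by events.

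The death and last-follow-up dates needed are already collected. Weighting by 30/90/180/365-day interval is optional. It needs dates of repeat admissions, whereas the data fields hold one date per event type plus a count.

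The cost is a few sentences, modest programming and slightly wider intervals. If Addendum 1 already contains such a method, cross-reference it and align the protocol and SAP 7.1 with it.
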